7.1.4 Rationale and Definition of Poor Scores for the Primary Estimand

The majority of the clinical endpoints in this study, including the co-primary endpoints, are defined for a range of values which have a defined minimum and maximum value. For these endpoints, a worst score can be defined based on the maximum, or minimum, score in the range depending on which value represents a worst score. The analyses of interest are based on a comparison of the change from baseline values for these endpoints. Given the assignment of a worst score, i.e., the most extreme value possible for an endpoint, the magnitude of the change score depends directly on the baseline value. For subjects with lower baseline scores, reflective of mild or moderate CRS, the resulting change score may be too extreme and not reflective of a change that is observed in the clinic. Consequently, a statistical analysis using these extreme values can result in subjects with unrealistic change scores; even a few such subjects can have a large, unintended influence on the assessment of treatment effect. In this sense, assignment of a worst score can produce a change score that is artificial and arbitrary, and this approach is not recommended ([O'Kelly & Ratitch, 2014](#)).

Instead, a ‘poor score’ ([O'Kelly & Ratitch, 2014](#)) is assigned to subjects with intercurrent events (1) and (2) defined above based on the upper 97.5th percentile of the distribution of the change scores observed in the clinic. The definition of a poor score and documentation of pre-specified poor scores assigned to each clinical endpoint is provided in the SAP Addendum, *Blinded Review of Clinical Endpoints in CRS for Assignment of Poor Scores* (26 October 2021).

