#### **9.3.3 Primary Estimand**

The primary efficacy estimand is the difference between each active treatment of twice-daily doses of 186 µg and 372 µg of OPN-375 and placebo for each of the co-primary endpoints.

For the primary estimand, intercurrent events will be addressed as follows:

1. Systemic corticosteroids use for CRS exacerbation or worsening of CRS nasal/sinus symptoms: a composite strategy will be employed with a poor score assigned to this event.
  - For CSNS, a value of '9' will be assigned. For APOV, a poor score is defined as follows: for a subject with a baseline APOV  $\geq 75\%$ , a value of '100%' is assigned; if baseline APOV  $< 75\%$ , a poor score is defined as baseline APOV + 25%. The rationale for assignment of a poor score is provided in the SAP. Also, further detail regarding the handling of a missing within-instrument data in these endpoints is provided in the SAP.
  - Systemic corticosteroid use for other indications will be considered a treatment and study discontinuation event (reference criteria 3).
2. Nasal surgery: composite strategy with poor scores assigned as above.
3. Treatment Discontinuation: treatment policy strategy; subjects may continue in the study until one of the following three mutually exclusive outcomes:
  - a. Subject completes Week 24/ET CT scan. In the absence of an intercurrent event (systemic corticosteroids, nasal surgery) use the endpoint value;
  - b. An intercurrent event (systemic corticosteroids for CRS exacerbation or worsening of CRS nasal/sinus symptoms, nasal surgery) occurs: Use composite strategy and assign poor score as described above (reference criteria 1,2);
  - c. Subject discontinues the study. Missing data due to study discontinuation following treatment discontinuation will be imputed; further detail on the imputation method is provided in the estimation section for each of the co-primary endpoints.

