7.1.3 Primary Estimand

The primary efficacy estimand is the difference between each active treatment of twice-daily doses of 186 μg and 372 μg of OPN-375 and placebo for each of the co-primary endpoints.

For the primary estimand, intercurrent events will be addressed as follows:

1. Systemic corticosteroids use for CRS exacerbation or worsening of CRS nasal/sinus symptoms: a composite strategy will be employed with a poor score assigned to this event.

For CSNS, a value of '9' will be assigned; further detail regarding the assignment of a worst score to the diary data are provided in Section 9.3.1. For APOV, a poor score is defined as follows: for a subject with a baseline APOV $\geq 75\%$, a value of '100%' is assigned; if baseline APOV $< 75\%$, a poor score is defined as baseline APOV + 25%.

The rationale for assignment of a poor score is provided in Section [7.1.4](#) below. Further detail regarding the handling of a missing POV in individual sinuses is provided in Section [9.3.2](#).

Systemic corticosteroid use for other indications will be considered a treatment and study discontinuation event (reference criteria 3c).

2. Nasal surgery: composite strategy with poor scores assigned as above.
3. Treatment Discontinuation: treatment policy strategy; subjects may continue in the study until one of the following three mutually exclusive outcomes:
 - a) Subject completes Week 24/ET CT scan. In the absence of an intercurrent event (systemic corticosteroids, nasal surgery) use the endpoint value;
 - b) An intercurrent event (systemic corticosteroids for CRS exacerbation or worsening of CRS nasal/sinus symptoms, nasal surgery) occurs: use composite strategy and assign poor score as described above (reference criteria 1, 2);
 - c) Subject discontinues the study. Missing data due to study discontinuation following treatment discontinuation will be imputed; further detail on the imputation method is provided in Section [7.1.5](#) for each of the co-primary endpoints.

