Table 9.1 displays the efficacy windows defined for the 7-day average Daily Nasal Symptoms diary and CSNS for each study week from baseline (Visit 2) through Week 12 (Visit 5).

The 7-day average diary score will be derived for each nasal symptom (range 0-3) and CSNS (range 0-9) by time point (AM or PM) and measure (instantaneous or reflective). Thus, there are sixteen 7-day average scores representing the individual nasal symptoms scores: 2 (AM, PM) * 2 (instantaneous, reflective) * 4 nasal symptoms (congestion, discharge, facial pressure, sense of smell), and there are four 7-day average CSNS scores: 2 (AM, PM) * 2 (instantaneous, reflective).

The 7-day average AM, instantaneous CSNS score is the primary efficacy variable in this study.

Missing Diary Data

On any given study day, for time (AM, PM), or measure (instantaneous, reflective), if any of the 3 nasal symptom scores is missing then the CSNS score will be missing for that study day, time, and measure. For both individual symptoms and the CSNS, the average 7-day value will be missing only if there are missing values for all 7 days. For the first week (Study Days 2-6, Table 9.1), the average 5-day value will be missing only if there are missing values for all 5 days.

Intercurrent Events (IE)

If an intercurrent event occurs, under the composite strategy per the primary estimand, a worst score of '3' will be assigned to each of the daily nasal symptoms scores recorded on the day of the IE and for the remaining days in the week in which the IE occurs; that is, the 7-day average score will include actual scores for days up to the IE and then a worst score for diary days recorded on or after the day of the IE. Since CSNS is a composite score as defined above, a worst score of '9' is assigned. Subsequent 7-day average scores will be assigned a worst score for the remainder of the CSNS study period.

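### SAP 7.1.4 advises against worst scores for the co-primaries, yet CSNS is assigned its scale maximum of 9 with no exception stated in the supplied documents, and no planned analysis applies the 7.1.4 rule to CSNS

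*SAP*

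**What the plan says.** **Assigned scores.** SAP 7.1.3 uses a composite strategy for systemic steroid use for CRS and for nasal surgery. On the symptom endpoint it reads "For CSNS, a value of '9' will be assigned; further detail regarding the assignment of a worst score to the diary data" and points to 9.3.1. APOV gets baseline plus 25 points, or 100% if baseline is 75% or more. The section then says "The rationale for assignment of a poor score is provided in Section" 7.1.4. Protocol 9.3.3 has the same order: "For CSNS, a value of '9' will be assigned. For APOV, a poor score is defined as follows", and after the APOV definition, "The rationale for assignment of a poor score is provided in the SAP".

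**Rationale.** SAP 7.1.4 names the co-primaries among the bounded endpoints it discusses. It says that "assignment of a worst score can produce a change score that is artificial and arbitrary, and this approach is not recommended", and that subjects with these two events instead receive a poor score "based on the upper 97.5th percentile of the distribution of the change scores observed in the clinic". It refers to an addendum of 26 October 2021 for the scores endpoint by endpoint; that addendum was not supplied.

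**Mechanics.** SAP 9.3.1 gives the CSNS range as 0–9 and says "Since CSNS is a composite score as defined above, a worst score of '9' is assigned". In the week of the event, "the 7-day average score will include actual scores for days up to the IE and then a worst score" from the event day on; later weeks are scored at the worst value throughout. SAP 7.5.1 repeats the 9, and SAP 7.3 carries the primary handling over to the pooled key secondary CSNS endpoint.

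**SIT.** SAP 7.5.11 assigns 10 after an event. SAP 9.3.10 gives the scale as 0–40, higher being better.

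**The concern.** With 9 assigned, the CSNS change is 9 minus baseline, so the mildest subjects receive the largest worsening. That is the dependence on baseline that 7.1.4 objects to, and it warns that a few such subjects can distort the treatment effect. APOV is protected from this; CSNS, tested first in the hierarchy of SAP 7.4, is not.

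The planned CSNS analyses do not close the gap:

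- Observed cases (SAP 7.2.3) uses observed values and assigns nothing.
- The supplementary estimand (SAP 7.2.1) removes the 9 for steroid use, keeps it for surgery and adds it for treatment discontinuation.
- The per-protocol analysis (SAP 5.6, 7.7) may simply exclude these subjects.
- The ranked analysis (SAP 7.2.2) covers APOV only. APOV is therefore seen under both a poor and a worst score; among assigned-score analyses, CSNS is seen only under the worst score.

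For SIT the problem is one of sign: a subject who starts below 10 and has the event is credited with a gain.

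**Working it through.** **1. The plan's own figures (SAP 4.2).** 111 per group, two-sided 5%. Power = Φ(δ/σ × √(n/2) − 1.96). CSNS: 0.8/1.9 × √55.5 − 1.96 = 1.18, power 88.0%. APOV: 11.3/27 × √55.5 − 1.96 = 1.16, power 87.7%. The stated 88% reproduces and is not in dispute.

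**2. Is 9 the maximum?** Three symptoms scored 0–3 (SAP 9.3.1): 3 × 3 = 9. Yes.

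**3. Size of one assigned score, in planning SDs.** APOV: at most 25/27 = 0.93. CSNS, event on or before Day 21, so that the whole Week 4 window (Days 21–27, SAP Table 9.1) is scored 9: (9 − b)/1.9.

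| Baseline b | Change | SDs |
|---|---|---|
| 3 | +6 | 3.2 |
| 4 | +5 | 2.6 |
| 5 | +4 | 2.1 |
| 6 | +3 | 1.6 |
| 7 | +2 | 1.1 |

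It equals the APOV maximum at b = 9 − 0.926 × 1.9 = 7.2.

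**4. Later events are diluted.** For an event on Day d in 21–27, with pre-event scores assumed equal to baseline, change = (28 − d)/7 × (9 − b). At b = 4: Day 22 +4.3, Day 24 +2.9, Day 25 +2.1, Day 26 +1.4, Day 27 +0.7. Events from Day 28 on do not affect the Week 4 score.

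**5. Compared with the 7.1.4 rule (illustration).** The documents give no CSNS percentile, mean baseline or event rate. Assume normal change with SD 1.9 and mean 0, −1 or −2. The 97.5th percentile is k = 1.96 × 1.9 + mean = 3.72, 2.72 or 1.72. The excess of the 9 is 9 − min(9, b + k):

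- b = 4: 1.28, 2.28, 3.28
- b = 5: 0.28, 1.28, 2.28
- b = 6: 0, 0.28, 1.28

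Divided by 111, one full-week event at b = 4–5 moves an arm mean by 0.0025 to 0.0295, which is 0.3% to 3.7% of 0.8. At b = 6 it is 0% to 1.4%.

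**6. Effect on the comparison (illustration).** Assume event-free mean changes of −0.6 (placebo) and −1.4 (active), SD 1.9, and all event subjects at one baseline with full-week events. Arm mean = (1 − p)m + p × s and variance = (1 − p) × 1.9² + p(1 − p)(s − m)², where p is the event rate and s the assigned change.

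- 2% events per arm, b = 4.5: the difference is 0.784 under every rule. Power is 81.9% with the 9, 83.4% with +3.7 and 84.9% with +2.7.
- 5% placebo and 2% active, b = 4.5: the differences are 0.937, 0.913 and 0.883. The 9 adds 0.024 to 0.054, or 3.0% to 6.8% of 0.8.
- Extreme case, 2% per arm with every event subject at b = 1.5 (roughly the floor set by the congestion entry criterion, Protocol 4.1): power 74.6%, 83.4%, 84.9%.

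**7. SIT.** Change = 10 − b, which is positive for b = 0–9. A pure guesser answers 40 items with one correct choice in four: Binomial(40, 0.25), mean 10. P(X ≤ 9) = 0.440 and P(6–9) = 0.396, so 0.396/0.440 = 90% of those below 10 start at 6–9 and are credited with 1–4 points.

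**The case against.** **The 7.1.4 pointer may concern APOV only.** In both documents it follows the APOV definition, and the CSNS sentence has its own pointer to 9.3.1. This does not stand. The 9 sits under an item that opens by announcing a poor score for the event, and the next item applies the poor scores above to both endpoints. SAP 7.1.4 also names the co-primaries outright.

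**The 9 is deliberate.** This stands. It is stated the same way in Protocol 9.3.3 and SAP 7.1.3, 7.5.1 and 9.3.1. It follows from setting each daily symptom to 3, and it remained after Protocol Amendment 6.0 clarified the poor score. A reader might infer that the 9 is a drafting error; the documents do not support that. The unsupplied addendum may give the reason.

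**CSNS is already analysed without the 9.** This stands in part. A reader might infer that the CSNS result rests on the 9 in every analysis. It does not: observed cases drops it entirely and the supplementary estimand drops it for steroid use. Those analyses answer different questions, however, and neither shows CSNS under the rule the SAP recommends.

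**Few events count.** Also fair. Only events before Day 28 matter, systemic steroids are prohibited (Protocol 5.6.3) and planned sinonasal surgery is excluded (Protocol 4.2).

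**SIT has a stated reason.** A score of 10 is what chance produces and is consistent with total anosmia, and baselines of 6–9 lie within guessing noise. That explains the choice of 10 but does not justify recording an event as an improvement.

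**Conclusion.** SAP 7.1.4 and the CSNS assignment conflict, and the supplied documents do not reconcile them. The conflict does not make the co-primary invalid or the 9 wrong. The 9 is pre-specified and consistent, and a scale maximum can be defended as a composite-strategy score. What is missing is a stated exception and one analysis showing CSNS under the SAP's own rule.

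The effect on the trial result cannot be computed. It is probably small if events before Week 4 are few and baselines moderate to high. It grows with low baselines or unequal event rates: the 9 widens the difference when placebo has more events and narrows it when active has more. The figures in steps 5 and 6 rest on assumed normal changes, baselines and event rates and show scale only.

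The SIT point is separate and minor: a wrong sign by construction, likely in few subjects, on an endpoint with only a nominal p-value.

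**What to change.** **CSNS.** Keep 9 as the primary assignment. In SAP 7.1.4, name CSNS as an exception and give the reason, or cite the addendum if the reason is there. Before unblinding, pre-specify one sensitivity analysis that assigns min(9, baseline + blinded 97.5th percentile of CSNS change) from the event day on, within the same day-weighted average of 9.3.1. Run it for the co-primary and for the pooled key secondary.

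The cost is a few sentences, one percentile and one extra analysis per endpoint. The documents do not say whether the October 2021 review produced a CSNS percentile. SAP 4.5 reports that a blinded look at CSNS change has been made, so it can be taken from blinded data. The small downside is that in this analysis the composite no longer equals the sum of components scored at 3.

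**SIT.** In SAP 7.5.11, assign min(baseline, 10). This changes one line; subjects with baseline 10 or above are unaffected and those below it get a change of zero.

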7.1.5 Estimator and Estimation Method - Primary Efficacy Analysis

Estimator and estimation method (CSNS): For the co-primary endpoint CSNS, the estimator is the mean difference between treatments (active versus placebo) in change from baseline to the end of Week 4 in the 7-day average instantaneous AM CSNS. Estimation is based on a mixed-effects model for repeated measures (MMRM) where changes from baseline to Week 2 and Week 4, in the 7-day average instantaneous AM CSNS, respectively, are the repeated measures. The 7-day windows used to define the 7-day average instantaneous AM CSNS from baseline through Day 84 (Week 12) are provided in Section 9.1.2.1, Table 9.1. The MMRM model will employ Restricted Maximum Likelihood (REML) for parameter estimation and the Kenward-Roger method for calculating the denominator degrees of freedom. An unstructured covariance matrix will be used to estimate within-subject error. For the treatment policy estimand, (reference Section 7.1.3, criteria 3,c), missing data due to study discontinuation will be estimated within the MMRM model under the assumption that the missing data are missing at random (MAR) and that early discontinuation from the study (prior to Week 4) is unlikely to reflect a treatment effect. Contingencies in the event of an issue with MMRM model convergence are described in Section 10.5.

The MMRM model will include categorical effects for previous sinus surgery (Y,N), nasal polyp status (present, absent), treatment (OPN-375 186 µg, OPN-375 372 µg, placebo), Week (2, 4), treatment-by-day interaction, and the continuous covariate: baseline 7-day average total instantaneous AM CSNS, with baseline-by-day interaction. The model-based LS mean difference between each active treatment group and placebo (active-placebo), 95% CI, and p-value will be displayed.

Estimator and estimation method (APOV): For the co-primary endpoint APOV, the estimator is the mean difference between treatments (active versus placebo) in the change from baseline to Week 24/ET APOV. Estimation is based on an ANCOVA model including categorical effects for previous sinus surgery (Y, N), nasal polyp status (present, absent), treatment (OPN-375 186 µg, OPN-375 372 µg, placebo), and baseline APOV. The model-based LS mean difference between each active treatment group and placebo (active-placebo), 95% CI, and p-value will be displayed.

For the treatment policy estimand, (reference Section 7.1.3, criteria 3, c), missing data due to study discontinuation will be imputed with a pattern mixture model (PMM) multiple imputation (MI) using the Jump-to-Control (J2C) method. The PMM assumes that the missing data at Week 24/ET on the control arm (placebo) is MAR, and the missing data on the active treatment arms have the profile of the control arm at Week 24/ET.

Multiple imputation using a PMM with J2C method will be conducted using the sequential modeling method as described in (O'Kelly & Ratitch, 2014). Further detail on the MI implementation, and statistical analysis and inference is provided in Section 10.

7.2 Sensitivity Analyses

7.2.1 Supplementary Estimand

A sensitivity analysis of the co-primary endpoints based on an alternative estimand will be performed.

Supplementary estimand: the difference between each active treatment of twice-daily doses of 186 µg and 372 µg of OPN-375 and placebo in each of the co-primary endpoints, irrespective of systemic corticosteroid use.

That is, for the supplementary estimand, intercurrent events will be addressed as follows:

1. Systemic corticosteroids use for all indications: treatment policy strategy; consider outcomes irrespective of systemic corticosteroid use; subjects may continue in the study until one of the following two mutually exclusive outcomes:
 - a) Subject completes Week 24/ET scan, use the endpoint value;
 - b) Subject discontinues the study. Missing data due to study discontinuation following treatment discontinuation will be imputed; further detail on the imputation method is provided in Section 7.1.5 for each of the co-primary endpoints.
2. Nasal surgery; i.e., study discontinuation for nasal surgery: composite strategy with poor scores assigned.
3. Treatment discontinuation: composite strategy with poor scores assigned.

For the supplementary estimand, the estimator and estimation methods for the co-primary endpoints, as well as the composite strategy with poor score assignments, are the same as for the primary estimand described above.

7.2.2 ANCOVA on Ranked APOV Values

A sensitivity analysis of the primary estimand and APOV co-primary endpoint will be performed based on ranked APOV values after modification of the primary estimand as follows. For the composite strategy, a worst score of 100% is assigned; for the treatment policy strategy, baseline APOV is assigned (BOCF). Baseline and endpoint APOV values are then ranked. Ranked APOV values will be analyzed with an ANCOVA model including categorical effects for previous sinus surgery and treatment. The method described by Koch, et. al. (1982) using extended Mantel-Haenszel statistics will be used to perform nonparametric treatment comparisons, adjusting for the baseline covariate. Implementation of this method is described in Stokes, et. al., Chapter 7 (2012).

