4.2 Design considerations for Sample Size and Power

Sample size assumptions for CSNS were based on previous Phase 3 studies of OPN 375 in subjects with nasal polyposis. Sample size assumptions for APOV were based on data from a study evaluating the change in maxillary and ethmoid opacification in chronic sinusitis patients treated with an intramuscular dose of triamcinolone (Pallanch 2013).

Based on the results for changes from baseline in morning symptoms among subjects with nasal polyps in the previous studies conducted with OPN 375, a sample of 111 subjects per group (333 total subjects) is sufficient to detect a -0.8 scale difference in morning symptoms score between treatments (OPN 375 vs placebo) using a 2-sided test at the 5% significance level with 88% power, and assuming a standard deviation of 1.9.

This sample size is also adequate to detect an -11.3% difference between treatments in average percent opacification using a 2-sided test at the 5% significance level with 88% power, and assuming a standard deviation of 27 percent.

The sample size was estimated for the co primary efficacy endpoints using Power Analysis and Sample Size Software (PASS 15) (NCSS, 2017).

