4.4 Randomization Stratification Factors

There are two stratification factors for randomization: 1) presence of nasal polyps of grade 1 or larger at baseline (Present vs Absent) and 2) previous sinus surgery (Yes vs No).

Both factors will be included in the analysis model as categorical covariates. In the event that a stratification error occurs, i.e., a subject is incorrectly stratified, in the primary analyses the subject will be analyzed as randomized (stratified), consistent with the ITT principle. The error will be documented as a major protocol violation and these subjects will be removed from the per-protocol analyses.

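### The rank-based sensitivity analysis of APOV leaves out nasal polyp status, a randomisation stratum and primary-model term, without saying why; the test is mildly conservative if polyp status is prognostic

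*SAP*

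**What the plan says.** SAP 4.4 names two randomisation strata, nasal polyps (present or absent) and previous sinus surgery (yes or no), and adds: "Both factors will be included in the analysis model as categorical covariates".

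The primary APOV analysis in SAP 7.1.5 does this: "Estimation is based on an ANCOVA model including categorical effects for previous sinus surgery (Y, N), nasal polyp status (present, absent), treatment", with baseline APOV as the remaining term. Protocol 9.3.4 has the same model.

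SAP 7.2.2 then plans a rank-based check: "A sensitivity analysis of the primary estimand and APOV co-primary endpoint will be performed based on ranked APOV values after modification of the primary estimand". It declares three changes: a score of 100% under the composite strategy, baseline carried forward under the treatment policy strategy, and ranking of the baseline and endpoint values. The model is then given as: "Ranked APOV values will be analyzed with an ANCOVA model including categorical effects for previous sinus surgery and treatment". Baseline enters through the Koch method, "using extended Mantel-Haenszel statistics will be used to perform nonparametric treatment comparisons, adjusting for the baseline covariate". Protocol 9.4.1 has the same text. Neither section mentions polyp status, and SAP 11 (changes from the protocol) does not explain its absence.

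**The concern.** A sensitivity analysis should differ from the primary analysis only in ways that the plan states, so that any disagreement can be traced. Here one of the two stratification factors drops out silently. The trial recruits subjects with and without polyps, stratifies on polyps and limits the polyp share, so polyp status is an odd factor to lose without comment.

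The statistical effect has a known direction. Stratified randomisation balances polyp status across arms. If polyp status predicts the outcome and is left out, its contribution stays in the residual variance although it no longer adds to the variability of the treatment difference. The test then rejects too seldom. The rank analysis is the only rank-based check among the APOV sensitivity analyses, and it could look weaker than the primary result partly for this reason.

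**Working it through.** **1. The models side by side**

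| Analysis | Surgery | Polyp status | Baseline |
|---|---|---|---|
| Primary APOV ANCOVA (SAP 7.1.5) | yes | yes | yes |
| APOV imputation model, control arm (SAP 10.2) | yes | yes | yes |
| Rank-based APOV check (SAP 7.2.2, Protocol 9.4.1) | yes | **no** | yes (Koch method) |

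The PGIC, QIDS severity and surgical-eligibility logistic models (SAP 7.5.8, 7.5.9, 7.6.1) and the stratified log-rank test (SAP 7.5.10) also keep both factors.

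**2. The plan's own power figure**

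SAP 4.2 plans 111 per group for an APOV difference of 11.3 percentage points, tested two-sided, and states: "at the 5% significance level with 88% power, and assuming a standard deviation of 27 percent".

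- SE = 27 × √(2/111) = 3.624
- Power = Φ(11.3/3.624 − 1.96) = Φ(1.158) = 0.877

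The stated 88% is reproduced.

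**3. Effect of omitting the stratum, by formula**

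Let p be the share with polyps and d the difference in mean APOV change between polyp strata, given baseline. The documents give no value for d, so 0 to 20 percentage points is an assumption. SD 27 is taken as the total, including the polyp component.

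- R² = p(1−p)d²/27²
- True type I error with the factor omitted = 2[1 − Φ(1.96/√(1−R²))]
- Power, omitted = Φ[(11.3 − 1.96·SE)/(SE·√(1−R²))]
- Power, included = Φ[11.3/(SE·√(1−R²)) − 1.96]

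Example with p = 0.5 and d = 20: R² = 0.25 × 400/729 = 0.137, and √(1−R²) = 0.929. Then 1.96/0.929 = 2.11, so the true type I error is 0.035.

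Results for p = 0.5, the polyp limit in Protocol 3.1 and SAP 3.1:

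| d | R² | Type I error, omitted | Power, omitted | Power, included |
|---|---|---|---|---|
| 0 | 0.000 | 0.050 | 0.877 | 0.877 |
| 5 | 0.009 | 0.049 | 0.878 | 0.879 |
| 10 | 0.034 | 0.046 | 0.881 | 0.887 |
| 15 | 0.077 | 0.041 | 0.886 | 0.901 |
| 20 | 0.137 | 0.035 | 0.894 | 0.919 |

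Protocol 3.3 implies a polyp share of about (333 − 125)/333 = 62%. With that share, type I error is 0.050, 0.049, 0.046, 0.042 and 0.036, and the power loss at 20 points is 0.916 − 0.893 = 2.3 points.

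**4. Check by simulation on ranks**

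There were 333 subjects, blocks within the four strata, and 372 µg compared with placebo, with 4,000 runs for type I error and 2,000 for power. Assumptions not in the documents: baseline APOV about 65 (SD 17), prior surgery in 50% of subjects with polyps and 30% without, values clipped to 0–100, no missing data or intercurrent events, and the Koch test run on ranks and residuals formed within strata.

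| Polyp share | d | Type I error, omitted / included | Power, omitted / included |
|---|---|---|---|
| 50% | 0 | 0.0522 / 0.0528 | 0.840 / 0.832 |
| 50% | 10 | 0.0455 / 0.0500 | 0.830 / 0.830 |
| 50% | 20 | 0.0392 / 0.0540 | 0.850 / 0.876 |
| 62% | 0 | 0.0500 / 0.0492 | 0.850 / 0.840 |
| 62% | 10 | 0.0508 / 0.0562 | 0.838 / 0.846 |
| 62% | 20 | 0.0360 / 0.0468 | 0.873 / 0.888 |

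Monte Carlo standard errors are about √(0.05 × 0.95/4000) = 0.003 for type I error and √(0.85 × 0.15/2000) = 0.008 for power. Both versions use the same simulated trials, so their differences are steadier than the separate figures. A rank ANCOVA in the same simulation gave 0.034 to 0.040 omitted against 0.047 to 0.055 included at 20 points, with 2.6 to 2.7 points of power lost. At d = 0, adding the factor cost the rank ANCOVA no power and the four-cell Koch test about 1 point.

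**The case against.** The strongest case on the other side has five parts.

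- **SAP 4.4 may not apply.** It speaks of one analysis model, and its next sentence concerns the primary analyses. Read that way, the primary model complies and SAP 7.2.2 contradicts nothing. A reader might infer a flat contradiction, but the text does not force it. The unexplained difference from SAP 7.1.5 remains either way. Protocol and SAP agree with each other, so this is not a mismatch between documents.
- **Attribution is already mixed.** A reader might infer that the missing covariate is what prevents a disagreement being put down to distributional assumptions. That is too strong. The declared 100% score replaces baseline + 25 points (or 100% from a baseline of 75%), and baseline carried forward replaces jump-to-control imputation, so the comparison was never purely distributional. What stands is that the omission adds one more difference, and an undeclared one.
- **No decision depends on it.** The rank analysis is outside the testing hierarchy in SAP 7.4 and carries no alpha. This stands.
- **Polyp status is covered elsewhere.** The supplementary, observed-cases, tipping-point and per-protocol analyses use the primary model or methods, and SAP 7.8 gives APOV results by polyp status with an interaction test. This stands, and it leaves the rank analysis as the exception.
- **The size is assumed.** No polyp effect on APOV change is documented, and up to 10 points the power difference is within simulation error. This stands: the test is not conservative unconditionally.

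**Conclusion.** The omission is real and unexplained, and its consequence is small. Polyp status is a randomisation stratum and a primary-model term, and SAP 7.2.2 and Protocol 9.4.1 drop it without listing this among their modifications. It also departs from SAP 4.4 if that sentence reaches beyond the primary model.

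The cost depends on how far polyp status predicts APOV change given baseline. It is nil at 0 points and under 1 point of power at 10. At 20 points, the far end of the assumed range, type I error is 0.035 to 0.04 and the power loss reaches about 2.5 points. Any error is in the conservative direction. The documents do not support reading this as inflated type I error or as a threat to the primary APOV result, which rests on a model that includes both factors.

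**What to change.** In both SAP 7.2.2 and Protocol 9.4.1, before unblinding:

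- add nasal polyp status to the ranked ANCOVA;
- stratify the extended Mantel-Haenszel comparison by polyp status as well as previous sinus surgery, which gives the four randomisation cells, with ranked baseline APOV as the covariate.

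The rule for how values are ranked need not change to meet this point. If the omission is deliberate, a sentence giving the reason and listing it with the other modifications would remove the inconsistency, but not the conservatism.

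Cost: a short text edit in each document, one extra stratification variable in the program, and at most about 1 point of power if polyp status turns out not to be prognostic.
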